4.1.4. Pharmacokinetics PK Endpoints

Trough concentration of pegozafermin.

4.1.5. Safety Endpoints

- Frequency and severity of TEAEs and SAEs
- Number of subjects who discontinued due to TEAEs and due to related TEAEs
- Incidence and shifts of clinically significant physical examination findings, ECG data and laboratory abnormalities; safety laboratory evaluations include hematology, blood biochemistry and urinalysis, serum, salivary, and urinary cortisol as appropriate
- Change from baseline in
 - Insulin-like growth factor 1 (IGF-1)
 - Bone biomarkers: Carboxy-terminal collagen crosslinks (CTX), N-terminal propeptide of type 1 collagen (P1NP) and osteocalcin
 - Thyroid stimulating hormone (TSH)
- Absolute and % change from baseline in lumbar spine, total hip, and femoral neck bone mineral density (BMD) as assessed by dual X-ray absorptiometry (DXA)
- Incidence and characteristics of anti-drug antibodies (ADA) and neutralizing antibody (NAb) after dosing (e.g., titer and binding specificity, to the FGF21 and polyethylene glycol [PEG] part of pegozafermin)
- Impact of the presence of ADAs on serum pegozafermin concentrations and clinical safety

4.1.6. Exploratory Endpoints

4.1.6.1. Change from baseline to Week 24 in the following clinical parameters

4.1.6.1.1. Histological assessments

Proportion of subjects at Week 24 with

- Fibrosis improvement ≥ 2 stage without worsening of NASH
- NASH resolution without worsening of fibrosis OR improvement of fibrosis ≥ 1 stage without worsening of NASH
- NASH resolution without worsening of fibrosis and ≥ 2 -point improvement in NAS score
- Improvement of fibrosis ≥ 1 stage without worsening of NASH and ≥ 2 -point improvement in NAS score
- At least a 2-point improvement in NAS with at least a 1-point improvement in ballooning or lobular inflammation, and no worsening of fibrosis
- Decrease >1 stage in fibrosis score

- At least 2-point improvement in NAS score AND are MRI-PDFF responders
- Fibrosis improvement ≥ 1 stage without worsening of NASH AND are MRI-PDFF responders AND ALT responders
- Fibrosis improvement ≥ 1 stage without worsening of NASH AND are MRI-PDFF responders
- Fibrosis improvement ≥ 1 stage without worsening of NAS score
- Fibrosis improvement ≥ 1 stage and cT1 reduction by ≥ 80 msec
- NASH resolution without worsening of fibrosis AND are MRI-PDFF responders AND ALT responders
- NASH resolution without worsening of fibrosis AND are MRI-PDFF responders
- NASH resolution and cT1 reduction by ≥ 80 msec
- Change from baseline in:
 - NAS total score
 - Fibrosis score

In MRI-PDFF responders

Proportion of patients with

- Fibrosis improvement ≥ 2 stage without worsening of NASH
- NASH resolution without worsening of fibrosis, OR improvement of fibrosis ≥ 1 stage without worsening of NASH
- NASH resolution AND fibrosis improvement ≥ 1 stage
- At least a 2-point improvement in NAS with at least a 1-point improvement in ballooning or lobular inflammation AND no worsening of fibrosis
- At least a 2-point improvement in NAS with at least a 1-point improvement in ballooning or lobular inflammation AND fibrosis improvement ≥ 1 stage

Change from baseline in NAS score.

- Artificial intelligence (AI)-based histological analysis (PathAI).

4.1.6.1.2. Imaging assessments

- Hepatic fat content with
 - Percentage of subjects with $\geq 30\%$ relative reduction in hepatic fat fraction as assessed by MRI-PDFF at Weeks 12 and 24
 - Percentage of subject with $\geq 50\%$ relative reduction in hepatic fat fraction as assessed by MRI-PDFF at Weeks 12 and 24
 - MRI-PDFF $\leq 5\%$ at Weeks 12 and 24

- Absolute and percent change from baseline in hepatic fibro-inflammation as measured by Iron-corrected T1 (cT1) imaging
- Percentage of subjects with ≥ 80 msec relative reduction in hepatic fibro-inflammation as measured by Iron-corrected T1 (cT1) imaging at Weeks 12 and 24
- Absolute and percent change from baseline in Fibroscan Vibration-controlled transient elastography (VCTE) score (liver stiffness measurement) and CAP (steatosis)
- Absolute and percent change from baseline in liver and spleen volume
- Absolute and percent change from baseline in pancreatic fat percentage

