6.4. Measures to Minimize Bias: Randomization and Blinding

6.4.1. Randomization and Stratification

Main study: All subjects will be centrally randomized 16:8:6:24:15 to Placebo QW, Placebo Q2W, pegozafermin 15 mg QW, 30 mg QW and 44 mg Q2W, respectively. The randomization will be stratified by T2DM status (yes vs. no) and fibrosis stage (F2 vs. F3). For the purposes of stratification, subjects will be considered to be T2DM status positive if any of the following

criteria are met: current medical history of T2DM, current use of anti-glycemic medication(s) for T2DM, or screening laboratory values of $\geq 6.5\%$ for HbA1c or ≥ 126 mg/dL for fasting plasma glucose. The proportion of subjects enrolled with MRI-PDFF $<8\%$ may be limited at the Sponsor's discretion.

In the Extension study, subjects randomized to placebo QW in the Main study will be re-randomized 1:1 to pegozafermin 30 mg QW (n=21) or placebo (n=21).

All subjects will be centrally assigned to randomized IP using an Interactive Response Technology (IRT).

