- Centralized monitoring can be considered for data acquired by electronic data capture systems (e.g., electronic case report forms [eCRFs], central laboratory or electrocardiogram [ECG] data, electronic patient reported outcomes) that are in place or could be put in place, providing additional monitoring capabilities that can

supplement and temporarily replace on-site monitoring through remote evaluation of ongoing and/or cumulative data collected from study sites, in a timely manner.

- Off-site monitoring can be conducted and will include phone calls, video visits, e-mail, or other online tools to discuss the study with the Investigator and site staff. Remote monitoring should be focused on review of critical study site documentation and source data. These activities could be used to get information on the clinical study progress, to exchange information on the resolution of problems, review of procedures, study subject status, as well as to facilitate remote site selection and Investigator training for critical study procedures.

Risk Mitigation

The Sponsor will continually assess whether the limitations imposed by the COVID-19 public health emergency on protocol implementation pose new safety risks to study subjects, and whether it is feasible to mitigate these risks by amending study processes and/or procedures.

10.7. Appendix 7: Prescreening Criteria for Identifying Potential Subjects with NASH and Stage 2 or 3 Fibrosis

To minimize unnecessary biopsies and help sites identify subjects at high risk for NASH with Stage 2 or 3 fibrosis (per NASH CRN system), the Sponsor recommends that screening liver biopsy decisions be based on the following prescreening criteria.

These guidelines are not inclusionary protocol requirements but are recommendations that Investigators can use when considering whether a potential subject should be screened for the study. All efforts should be made to ensure that noninvasive procedures are performed prior to the liver biopsy.

Consult with the Medical Monitor (or designee) if clarification is needed on whether a potential subject should be considered for the study.

1. **Increased metabolic risk:** potential subjects with at least 2 of the criteria as part of their medical history are at increased metabolic risk:
 - a. Central obesity: Waist circumference of >102.0 cm for males, >88.0 cm for females, or body mass index (BMI) >25.0 kg/m². BMI should not exceed 50.0 kg/m².

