4.1.6.1.4. Laboratory parameters

- Percentage of subjects with ≥ 17 U/L decrease in ALT
- Percentage of subjects with $\geq 30\%$ decrease in ALT
- AST
- Gamma-glutamyl transpeptidase (GGT)
- Alkaline phosphatase (ALP)
- Fasting glucose
- C-peptide
- Fasting insulin
- Adipo-IR index (fasting free fatty acids x fasting insulin)
- Homeostatic model assessment for insulin resistance (HOMA-IR)
- Enhanced liver fibrosis (ELF) score
- Fibrosis-4 (FIB-4) index
- Absolute and percent change from baseline in HbA1c in subjects with baseline HbA1c $\geq 6.5\%$

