6. ANALYSIS POPULATIONS

For purposes of analysis, the following populations are defined:

Population	Description
Randomized Analysis Set	All enrolled subjects who are assigned a randomization number in the study.
Full Analysis Set (FAS)	All enrolled subjects with confirmed fibrosis stage F2 or F3 and NAS ≥ 4 at baseline per independent review by a 3-pathologist panel who are eligible and assigned a randomization number in the study and received at least 1 dose of IP. For analysis purposes, subjects will be analyzed according to the treatment they were randomized to regardless of actual treatment received.
Safety Analysis Set	All randomized subjects who receive at least 1 dose of IP. In this population, subjects will be summarized based upon the IP actually received, regardless of the IP to which they were randomized.
PK Analysis Set	All subjects in the FAS who have sufficient data to adequately characterize the trough serum pegozafermin concentrations and have no other events or protocol violations that would adversely affect results, such as not completing the full dose. The analysis population for any population PK modeling may be defined separately in a population PK data analysis plan.
MRI-PDFF Analysis Set	All subjects in the Full Analysis Set who have a baseline and at least one follow up MRI-PDFF assessment.

Primary Analysis

- Patient dispositions and screen failure summary will be presented for all subjects screened.
- Baseline characteristics, protocol deviations, medical histories and concomitant medications will be assessed for Randomized Analysis Set.
- All primary, secondary, and exploratory efficacy endpoints of Main Study will be assessed for Full Analysis Set.
- Exposure and safety assessments will be analyzed based on Safety Analysis Set.
- PK endpoints will be displayed and analyzed for all subjects with applicable data in the PK Analysis Set.

Final Analysis

- Protocol deviations and concomitant medications will be summarized based on Randomized Analysis Set including data in Extension Study.
- Exposure and safety assessments will be summarized based on Safety Analysis Set including data in Extension Study.
- PK endpoints will be displayed and analyzed for all subjects with applicable data in the PK Analysis Set.

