7.8.3. Exploratory Efficacy Analysis

All other exploratory efficacy endpoints listed in Section 4.1.6 will be analyzed based on Full Analysis Set with confirmed fibrosis stage F2 or F3 and NAS ≥ 4 at baseline per 3-panel consensus read unless otherwise specified. Subject FAST score defined below will also be analyzed.

$$\text{FAST} = \{\exp(-1.65 + 1.07 \times \ln(\text{LSM}) + 2.66 \times 10^{-8} \times \text{CAP}^3 - 63.3 \times \text{AST}^{-1})\} / \{1 + \exp(-1.65 + 1.07 \times \ln(\text{LSM}) + 2.66 \times 10^{-8} \times \text{CAP}^3 - 63.3 \times \text{AST}^{-1})\}$$

For all proportion endpoints, the same stratified CMH methodology as the analysis of primary efficacy endpoints (described in Section 7.8.1) will be used to compare the differences of responder rate in each pegozafermin group versus placebo.

For change from baseline and percent change from baseline endpoints listed Section 4.1.6, descriptive summaries of absolute value and change from baseline at Week 24 will be provided. If there is only a single scheduled post-baseline assessment in Main Study, change from baseline will be analyzed by analysis of variance (ANCOVA) with treatment group, baseline measurement, and two stratification factors as covariates. Otherwise, MMRM method will be used as described in Section 7.8.2. Same as secondary efficacy endpoints, non-parametric van Elteren test stratified by T2DM status (yes vs. no) and fibrosis stage (F2 vs. F3) will be performed if the MMRM (ANCOVA) model assumptions are severely violated. The location shift estimate, and Hodges-Lehmann 2-tailed 95% confidence interval will be presented. For the comparison between each pegozafermin group and placebo, if small cell counts (<5) render the van Elteren test inappropriate, the un-stratified Wilcoxon rank-sum test will be used instead.

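### The exploratory MRI-PDFF ≤5% endpoint has no baseline condition, so a subject who enters at or below 5% and stays there counts as a responder without any reduction in liver fat

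*SAP*

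**What the plan says.** **Endpoint.** Among the exploratory imaging endpoints, SAP 4.1.6.1.2 lists "MRI-PDFF $\leq 5\%$ at Weeks 12 and 24". The two items just above it count subjects with at least a 30% or 50% "relative reduction in hepatic fat fraction as assessed by MRI-PDFF at Weeks 12 and 24". The ≤5% item asks only for a level at the visit.

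**Analysis set and test.** SAP 6 states: "All primary, secondary, and exploratory efficacy endpoints of Main Study will be assessed for Full Analysis Set". SAP 7.8.3 agrees: "All other exploratory efficacy endpoints listed in Section 4.1.6 will be analyzed based on Full Analysis Set", unless otherwise specified. SAP 7.8.2, on secondary endpoints, assigns MRI-PDFF to the MRI-PDFF Analysis Set and does not say whether that extends to exploratory MRI-PDFF endpoints. On the test, 7.8.3 says: "For all proportion endpoints, the same stratified CMH methodology as the analysis of primary efficacy endpoints" will be used. That method (SAP 7.8.1) is stratified by diabetes status and fibrosis stage and reports differences in proportions.

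**Entry.** The eligibility criteria (Protocol 5.1 and 5.2) contain no MRI-PDFF minimum. Three passages bear on low liver fat:

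- Inclusion criterion 3 requires a biopsy steatosis score of at least 1. Protocol 8.1.1 defines grade 1 as more than 5% and up to 33%.
- Protocol 6.4.1: "The proportion of subjects enrolled with MRI-PDFF $<8\%$ may be limited", at the sponsor's discretion.
- Protocol Appendix 7 (Section 10.7) suggests MRI-PDFF of at least 5.0% or CAP of at least 250 dB/m as signs of steatosis, but says: "These guidelines are not inclusionary protocol requirements but are recommendations that Investigators can use".

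**The concern.** A responder endpoint defined by a level is informative about treatment only for subjects who start on the other side of that level. Here a subject whose MRI-PDFF goes from 4.0% to 5.0%, a rise of one quarter, is a responder. The same subject fails both relative-reduction endpoints in the same list.

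Two things are at stake. The rate at or below 5% in each arm would mix subjects who reached that level with subjects who were already there. The comparison with placebo would lose some of its contrast. The study is meant to inform Phase 3 dose selection (SAP 3.5), so it helps if arm-level rates do not depend on who entered with low liver fat.

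**Working it through.** **Step 1: can a subject at or below 5% enter?** Yes. The 8% limit is optional. Appendix 7 is advisory, and its steatosis item is met by CAP alone; a subject at exactly 5.0% meets both its MRI-PDFF item and the endpoint. The biopsy criterion is binding, but it is a histological grade rather than an MRI value, and a historical biopsy may be up to 6 months old. It lowers the chance without removing it.

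**Step 2: does either analysis set exclude such a subject?** No. The FAS requires F2 or F3, NAS ≥4, eligibility and one dose. The MRI-PDFF Analysis Set adds a baseline and at least one follow-up scan. Neither has an MRI-PDFF minimum, so the gap is the same whichever set applies.

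**Step 3: size on the planned scale.** The documents give no sample size, power or expected rate for this endpoint, so there is no stated figure to reproduce, and all inputs here are assumptions. Let f be the share of each arm at or below 5% at baseline, all of whom stay there. Let p be the true rate among the rest.

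Observed rate = f + (1−f)p. Observed difference = (1−f)(p_active − p_placebo).

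With p = 2% on placebo and 30% on active (true difference 28 points):

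| f | Placebo | Active | Difference | Loss |
|---|---|---|---|---|
| 2% | 0.02 + 0.98×0.02 = 4.0% | 0.02 + 0.98×0.30 = 31.4% | 0.98×28 = 27.4 | 0.6 |
| 5% | 0.05 + 0.95×0.02 = 6.9% | 0.05 + 0.95×0.30 = 33.5% | 0.95×28 = 26.6 | 1.4 |
| 10% | 0.10 + 0.90×0.02 = 11.8% | 0.10 + 0.90×0.30 = 37.0% | 0.90×28 = 25.2 | 2.8 |

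**Step 4: power, under assumed rates.** This uses the pooled-variance normal approximation for two proportions, two-sided 0.05, unstratified. As a check on the formula, with 15% dropout it gives 93.8%, 91.8%, 87.1% and 84.0% for the histology comparisons, where SAP 3.5 states 94%, 92%, 87% and 83%. Those figures are not in dispute.

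For the ≤5% endpoint, take 64 per arm, no dropout, and assumed rates of 5% and 30%. The restricted analysis has 64(1−f) per arm:

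| f | Power, all subjects | Restricted n per arm | Power, restricted |
|---|---|---|---|
| 2% | 95% | 62.7 | 97% |
| 5% | 91% | 60.8 | 96% |
| 10% | 84% | 57.6 | 95% |

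With assumed rates of 10% and 40% and f = 10%, the figures are 91% and 97%. The restriction gains more from removing uninformative responders than it loses in denominator.

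**The case against.** The strongest reply is that this is a legitimate description of a state, the share of subjects at or below 5% at a visit, and that neighbouring analyses already measure change. The same list has the 30% and 50% reduction endpoints. Absolute and percent change in MRI-PDFF is a secondary endpoint, modelled with baseline as a covariate. Every subject also needed histological steatosis to enter, so few or none may be affected. All of this stands, and it keeps the point minor. It does not make a subject who was already at the threshold informative when arms are compared.

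A reader might infer four stronger things that the documents do not support:

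- **That the SAP is inconsistent with its own HbA1c rule.** The item "Absolute and percent change from baseline in HbA1c in subjects with baseline HbA1c" of at least 6.5% is a continuous change in a subgroup. It is not a threshold responder endpoint, so it sets no precedent.
- **That the relative effect is badly distorted.** A ratio of rates would move more than the difference, especially if the assumed placebo rate is low. The SAP plans differences in proportions and no ratio.
- **That the 15 mg arm is specially exposed.** One subject in 16 is 1/16 = 6.25 points for every proportion endpoint in this trial.
- **That the definition favours the drug.** With similar shares in each arm the difference shrinks. Chance imbalance is possible, but it has no expected direction.

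**Conclusion.** The point holds as a cheap improvement to one exploratory endpoint. As written, a subject at or below 5% at entry who stays there is a responder without any reduction, and nothing in eligibility or in either analysis set prevents this. On the planned scale the loss is 0.6 to 2.8 points out of 28 for f between 2% and 10%.

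That size rests on assumed rates of 2% and 30%, on the same f in each arm, and on all such subjects staying at or below 5%. If some rise above 5%, they add fewer responders; if more of them rise on placebo than on active, the loss in the difference is smaller. The true f is not given and may be zero, in which case there is no effect. The primary, key secondary and continuous MRI-PDFF results do not depend on this definition.

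**What to change.** In SAP 4.1.6.1.2 and 7.8.3:

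- Restrict the MRI-PDFF ≤5% endpoint to subjects with baseline MRI-PDFF above 5%. The condition is fixed before randomisation, so the comparison remains a randomised one.
- State whether the FAS or the MRI-PDFF Analysis Set applies, since 7.8.2 and 7.8.3 differ.
- Report the number with baseline MRI-PDFF at or below 5% by arm. The baseline table in SAP 7.4 plans only a cut at 8%, so this count would not otherwise appear.

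The cost is a line or two of SAP text and a slightly smaller denominator. If no subject starts at or below 5%, the restriction removes nobody.

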4.1.6.1.3. Anthropometric assessments

- Body weight
- Waist circumference
- Waist/hip ratio

4.1.6.1.4. Laboratory parameters

- Percentage of subjects with ≥ 17 U/L decrease in ALT
- Percentage of subjects with $\geq 30\%$ decrease in ALT
- AST
- Gamma-glutamyl transpeptidase (GGT)
- Alkaline phosphatase (ALP)
- Fasting glucose
- C-peptide
- Fasting insulin
- Adipo-IR index (fasting free fatty acids x fasting insulin)
- Homeostatic model assessment for insulin resistance (HOMA-IR)
- Enhanced liver fibrosis (ELF) score
- Fibrosis-4 (FIB-4) index
- Absolute and percent change from baseline in HbA1c in subjects with baseline HbA1c $\geq 6.5\%$

4.1.6.2. Change from baseline PRO scores at Weeks 12 and 24 in

- Chronic Liver Disease Questionnaire - NAFLD-NASH (CLDQ NAFLD-NASH)
- Questionnaire for NASH (WPAI-NASH)
- Europe Quality of Life Group 5 dimension 5 level questionnaire (EQ-5D-5L)

- Liver-related pain and discomfort questionnaire
- The appetite sensations visual analog scale (VAS)

4.2. Extension Study Endpoints

4.2.1. Primary Endpoints

- Frequency and severity of TEAEs and SAEs at Week 48

4.2.2. Secondary Endpoints

- Absolute change and percent change from baseline at Week 48 in liver parameters:
 - Hepatic fat fraction by MRI-PDFF
 - ALT
 - Pro-C3
- Trough concentration of pegozafermin

4.2.3. Safety Endpoints

- Number of subjects who discontinued due to TEAEs and due to related TEAEs
- Incidence and shifts of clinically significant physical examination findings, ECG data and laboratory abnormalities; safety laboratory evaluations include hematology, blood biochemistry and urinalysis, serum, salivary, and urinary cortisol as appropriate
- Insulin-like growth factor 1 (IGF-1)
- Bone biomarkers: Carboxy-terminal collagen crosslinks (CTX), N-terminal propeptide of type 1 collagen (P1NP) and osteocalcin
- Thyroid stimulating hormone (TSH)
- Absolute and % change from baseline in lumbar spine, total hip, and femoral neck bone mineral density (BMD) as assessed by dual X-ray absorptiometry (DXA)
- Incidence and characteristics of anti-drug antibodies (ADA) and neutralizing antibody (NAb) after dosing (e.g., titer and binding specificity, to the FGF21 and polyethylene glycol [PEG] part of pegozafermin)
- Impact of the presence of ADAs on serum pegozafermin concentrations and clinical safety
- Levels of endogenous FGF21 at the immunogenicity follow-up visit(s) compared to baseline in NAb positive subjects

4.2.4. Exploratory Endpoints

4.2.4.1. Mean and percent change from baseline at Weeks 38 and 48 in the following metabolic parameters:

- Adiponectin
- Serum triglycerides
- HDL-c, Non-HDL-c, LDL-c, HbA1c.

4.2.4.2. Change from baseline in the following clinical parameters:

4.2.4.2.1. Imaging assessment

- Change in hepatic fibro-inflammation as measured by cT1 imaging
- Change in FibroScan VCTE score (liver stiffness measurement) and CAP (steatosis)

4.2.4.2.2. Anthropometric assessments for

- Body weight
- Waist circumference
- Waist/hip ratio.

4.2.4.2.3. Laboratory parameters

- Percentage of subjects with ≥ 17 U/L decrease in ALT
- Percentage of subjects with $\geq 30\%$ decrease in ALT
- AST, GGT, ALP
- Fasting glucose
- C-peptide
- Fasting insulin
- Adipo-IR index (fasting free fatty acids x fasting insulin)
- HOMA-IR
- ELF score
- FIB-4 index

4.2.4.3. Change from baseline PRO scores at Weeks 48 in

- CLDQ NAFLD-NASH
- WPAI-NASH
- EQ-5D-5L
- Liver-related pain and discomfort questionnaire

- The appetite sensations VAS

A cross table of specified criteria and each exploratory endpoint is provided in ([Main Study exploratory proportion endpoints](#)).

4.3. Subgroups

Subgroup analysis will be performed in the following baseline subgroups for primary efficacy endpoints. If the percentage of patients within a subgroup is less than 33% of overall subjects and the number of patients in the subgroup is lower than 15, only descriptive analysis will be performed.

- Age group (21 - <65, \geq 65)
- Race (White, Non-white)
- Sex (Male, Female)
- Baseline BMI group (<30, 30 - <35, \geq 35 kg/m²)
- Baseline T2DM (Yes, No)
- Baseline Fibrosis stage (F2, F3)
- Baseline MRI-PDFF (<median, \geq median)
- Baseline ALT (normal, >ULN)
- Baseline NAS score (<median, \geq median)

